1.0 Research Design

1.1 Purpose/Specific Aims

The proposed study will integrate user-centered design, community engagement, and implementation science, with a randomized controlled trial (RCT), to develop, test, and collect implementation data on a youth-led HTN education digital badge. The badge will act as an electronic tool to guide youth through learning and then teaching adults on how to achieve better HTN control. Adults with HTN and youth from the local community will be recruited for user-centered design sessions to provide input in the development of a youth-led HTN education digital badge. We will then recruit adult ED patients with uncontrolled HTN (BP $\geq 130/80$ mm Hg) who have an existing relationship (such as family member) with a youth (14-24 years old) and the youth themselves for an RCT. The adult plus youth dyad will be randomized to either: 1) intervention arm- 6-week youth-led HTN education digital badge at home- or 2) control arm- 6-week youth job readiness digital badge at home. In addition to the primary study outcome of adult BP change 2-months post-intervention, we will collect secondary outcomes of HTN knowledge and youth self-efficacy, as well as implementation metrics of intervention acceptability, feasibility, and fidelity. Bringing health education to the patient's home, while simultaneously empowering youth is an innovative technology-driven model for improving BP for patients with uncontrolled HTN who may lack access to care. Outcomes of this project will result in a scalable and easily adoptable model to empower youth while simultaneously improving BP in a difficult to reach adult population.

Due to challenges recruiting youth through adults in the ED, we will be adding a cohort to the study. For this new cohort of the study, we will recruit interested youth from New Brunswick Health Sciences Technology High School (NBHSTHS). Students will be asked to pair themselves with an adult (18+) (preference for adult who has been diagnosed with hypertension, but not mandatory) with an existing relationship with the student where it would be feasible to complete an online module together 1 hour per week for 6 weeks. The adult must be fluent in English or Spanish and the student must be able to speak the fluent language of the adult. We will evaluate the youth-led digital hypertension (HTN) education intervention- an electronic tool to guide youth through learning and then teaching and supporting adults on how to control hypertension (for adults with hypertension) and how to avoid it (for adults without hypertension). Outcomes of interest are HTN knowledge, confidence in HTN management, and health behavior changes in participants, which will be obtained through pre- and post- intervention assessments. We will also be exploring outcomes of participant acceptability, feasibility, and fidelity of the intervention.

A. Objectives

Specific aims are:

Aim 1: Create a youth-led HTN education digital badge by means of user-centered design methods and community engagement with adults with HTN and youth to obtain input on the contents of the digital badge prior to implementation.

Aim 1a: The hypertension knowledge assessment being used in the study has not been used before on youth or Spanish-speaking populations, so we will obtain feedback on the assessment from these groups.

Aim 2: Evaluate the effectiveness of a youth-led HTN education digital badge intervention on the primary outcome of mean systolic BP (SBP) and diastolic BP (DBP) change in adults with uncontrolled HTN at 2-months post-intervention compared to the control group. Additionally, evaluate change in HTN knowledge and youth self-efficacy. Additionally, we will measure confidence in HTN management, and health behavior changes in participants.

Aim 3: Evaluate the implementation process of the youth-led HTN education digital badge by collecting qualitative and quantitative data on acceptability, feasibility, and fidelity of the intervention by participants.

B. Hypotheses / Research Question(s)

Research Question (Aim 1): *What are the most acceptable and easily understood ways to present HTN information to this population?*

Hypothesis 2abc (Aim 2): (a) The mean SBP and DBP differences at 2-month post-intervention will show greater decreases for the intervention group than the control group. (b) HTN knowledge will increase from pre- to post-intervention in youth and adults in the intervention group and will not change in control group. (c) Youth self-efficacy will increase from the pre- to the post-intervention period in both the intervention and control groups.

Hypothesis 3 (Aim 3): *The intervention will overall have high acceptability and feasibility (average scores of ≥ 4 on the Acceptability of Intervention Measure (AIM) and Feasibility of Intervention Measure (FIM) scales¹) and fidelity (majority will complete entire digital badge playlist correctly).*

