1.6 Study Variables

A. Independent Variables, Interventions, or Predictor Variables

Aim 1: Not applicable

Aim 1a: Not applicable

Aim 2: For the first cohort, outcomes will be compared for dyads randomized to the intervention arm versus those randomized to the control arm, where youth participants in the intervention arm will complete the youth-led HTN education digital badge with their hypertensive adult and youth participants in the control arm will complete job readiness digital badge(s).

For the school cohort, we will be looking at changes before and after the 6-week intervention in adult and youth participants.

Aim 3: Not applicable

B. Dependent Variables or Outcome Measures

Aim 1: Not applicable

Aim 1a: Not applicable

Aim 2: For the first cohort, the primary outcome is change in BP (in mm Hg) from baseline to 1 week and 2 months later. We will also collect secondary outcomes of pre- and post-intervention change in HTN knowledge, adult BP self-care, adult self-efficacy to manage HTN and youth confidence in managing adult BP during the same timepoints.

For the school cohort, outcomes of interest are HTN knowledge, confidence in HTN management, and health behavior changes in participants. (Same outcomes as the first cohort except for the BP change.)

Aim 3: Not applicable

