Aim 2: For the first cohort, BP data will be collected when the potential participant is in the ED by the recruiter- either the RA or PI and will be entered into the RedCap study database. It will then be collected at 1 week and 2 months post-intervention when the adult participant returns to RWJUH for follow-up BP readings which will be entered into RedCap. HTN knowledge, self-efficacy, and self-care data will be collected electronically via RedCap. Participants will be sent a link to the appropriate questionnaires to be completed at baseline, 1 week post intervention, and 2 months post intervention.

For the school cohort, data collection will be done through Redcap. Questionnaires will be completed in person at the school (youth) or remotely (adults).

Aim 3: All participants in the intervention group will be asked to complete a questionnaire at the end of each intervention module through the digital badge platform, which will allow them to complete the questionnaire in RedCap. Participants must complete the questionnaires to receive their digital badge incentive.

We will also conduct one-on-one phone/Zoom interviews with interested participants for more in-depth information on intervention acceptability, feasibility, and fidelity. Interviews will last approximately 30-45 minutes each, be available in English and Spanish, and be audio recorded. The audio recording will then be transcribed by the RA.

▪ **Timing and Frequency:**

Aim 1: Participation will be a one-time design session.

Aim 1a: Participation will be a one-time design session.

Aim 2: For the first cohort, BP will be collected at baseline in the ED and at 1 week and 2-month post-intervention follow-ups at RWJUH. HTN knowledge, self-care, and self-efficacy will be collected at the start of the intervention, and at 1 week and 2 months post-intervention.

For the school cohort, youth and adult participants will complete study assessments after consent is signed. Fidelity of the intervention will be collected on youth the following week, and

youth will complete a HTN knowledge assessment at the end of this session. At the end of each of the 6 intervention modules, participants will complete module feedback assessments. At the end of the 6-week intervention and then 1 month after the end of the 6-week intervention, all participants will complete study assessments.

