4.7 Risks of Harm/Potential for Benefits to Subjects

A. Description of Risks of Harm to Subjects

▪ Reasonably Foreseeable Risks of Harm

This is a minimal risk study. The only foreseeable risk of harm is a possible loss of confidentiality, however procedures will be in place to minimize risks of harm.

▪ Risk of Harm from an Intervention on a Subject with an Existing Condition

Not applicable

▪ Other Foreseeable Risks of Harm

None

▪ Observation and Sensitive Information

Not applicable

B. Procedures which Risk Harm to Embryo, Fetus, and/or Pregnant Subjects

Not applicable

C. Risks of Harm to Non-Subjects

Not applicable

D. Assessment of Social Behavior Considerations

Not applicable

E. Minimizing Risks of Harm

The PI is responsible for protecting the confidentiality of subjects' data. All data will be entered into electronic database (RedCap). RedCap is a secure, web-based application. There will be no paper charts/data entry. This will minimize the potential for loss of information and breach of privacy.

Patient confidentiality will be maintained through secured, password protection computerized data collection. All documents and information about this study will be kept confidential in accordance

with federal, state, and local laws and regulations. The results of this study will be published. If results are published, no subject will be identified by name.

- **Certificate of Confidentiality**

Not applicable

- **Provisions to Protect the Privacy Interests of Subjects**

Patient confidentiality will be maintained through secured, password protection computerized data collection. All documents and information about this study will be kept confidential in accordance with federal, state, and local laws and regulations. The results of this study will be published. If results are published, no subject will be identified by name.

F. Potential Benefits to Subjects

It is possible that adult participants with uncontrolled hypertension in the intervention arm of the randomized controlled trial (RCT) (Aim 2 first cohort) may experience a decrease in their blood pressure. We have also hypothesized that youth in both arms of the RCT (Aim 2 first cohort) may experience increased knowledge and self-empowerment. First the school cohort, participants may show an increase in hypertension knowledge, confidence in HTN management, and/or health behavior changes.

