6.0 Data Management Plan

6.1 Data Analysis

Aim 1: *Quantitative*: Questionnaire data will be analyzed descriptively. *Qualitative*: Audio recordings will be transcribed verbatim, and will be analyzed using Gale's Framework Method.⁴² As such, three members of the study team will conduct open coding for all transcripts and will meet to agree on a working analytical framework. Categories will be grouped into subsequent themes as related to the digital badge. The PI will then refine the digital badge based on findings from the design sessions with input from mentors.

Aim 1a: Qualitative data will be collected from youth on their feedback on the hypertension knowledge assessment tool. In addition, we will analyze item discrimination and internal reliability of the tool based on their completion of the tool in its entirety. Data from a brief demographic survey will be analyzed descriptively.

Aim 2: Descriptive statistics will be used to assess participant characteristics and covariate balance across study arms. To determine balancing of important measures that may influence outcome variables, the analysis will implement t-tests for continuous variables and chi-square tests for categorical variables. STATA will be used to carry out all statistical analysis. Analysis will include mean BP change from baseline to 2-month follow-up for each arm using a t-test. Multivariate linear regression analysis will also be used to compare the two groups, including a dummy variable for group, baseline BP, and any covariates found to be unbalanced across arms. For youth empowerment, pre- and post-intervention data will be compared with significance testing via t-test.

Aim 3: *Quantitative:* Quantitative data will be analyzed descriptively. *Qualitative:* Interviews will be analyzed using Gale's Framework Method⁴² (see Aim 1 for more details).

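### Hypothesis 2b on hypertension knowledge is worded as two within-arm statements, one of them no change in controls, and section 6.1 names no Aim 2 test for it

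*Combined protocol and SAP*

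**What the plan says.** Section 1.1 B states hypothesis 2b as: "HTN knowledge will increase from pre- to post-intervention in youth and adults in the intervention group and will not change in control group". Hypothesis 2a, directly before it, is put as a contrast at 2 months: blood pressure differences "will show greater decreases for the intervention group than the control group".

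Section 1.6 B makes knowledge a secondary outcome of the ED cohort: "We will also collect secondary outcomes of pre- and post-intervention change in HTN knowledge". Section 1.6 A says of that cohort that "outcomes will be compared for dyads randomized to the intervention arm versus those randomized to the control arm", without naming a method. Section 1.9 A gives two follow-ups: "HTN knowledge, self-care, and self-efficacy will be collected at the start of the intervention, and at 1 week and 2 months post-intervention".

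The Aim 2 paragraph of section 6.1 lists baseline balance tests, a t-test of blood pressure change, a regression, and a pre/post t-test for youth empowerment. The regression reads: "Multivariate linear regression analysis will also be used to compare the two groups, including a dummy variable for group, baseline BP". Hypertension knowledge does not appear there. The knowledge tool is mentioned in 6.1 only under Aim 1a, for item discrimination and reliability.

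Section 4.7 F, on benefits, says it was hypothesized that "youth in both arms of the RCT (Aim 2 first cohort) may experience increased knowledge and self-empowerment".

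**The concern.** The randomised design supports one question about knowledge: did the intervention arm end up knowing more than the control arm? Hypothesis 2b does not ask it. It predicts a rise in one arm and none in the other, and the obvious way to judge that is two separate pre/post tests. This has two faults.

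- A significant rise in one arm beside a non-significant one in the other does not show that the arms differ. If both arms gain equally, for example because the same questionnaire is taken repeatedly, chance alone can produce the predicted pattern.
- A non-significant control change does not show absence of change. That claim would need an equivalence margin, and none is given.

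Section 6.1 does not remove the ambiguity. Its regression names no outcome, but it follows the blood pressure sentence and adjusts for baseline blood pressure, so it reads as the blood pressure model. The only other non-BP outcome test in the paragraph, for youth empowerment, is itself a pre/post t-test. With two follow-ups and none named, the choice of time point is also open.

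At stake is a false claim that the badge raised knowledge, or that controls did not change.

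**Working it through.** **Text check.** There is no planned figure to reproduce: the documents give no alpha, power, effect size, SD, margin or allocation ratio, and section 1.5 defers sample size calculation to later studies.

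| Element | 2a (blood pressure) | 2b (knowledge) |
|---|---|---|
| Contrast between arms in the hypothesis | yes | no |
| Follow-up named in the hypothesis | 2 months | none; collected at 1 week and 2 months |
| Aim 2 test in 6.1 | t-test and regression | none |

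**Illustration, conditional on 2b being judged by a paired t-test in each arm, which the documents do not state.** Assumptions: two-sided 5%; 1:1 allocation; true change *d* in units of the SD of change; the same *d* in both arms and in youth and adults. Section 4.3 gives 100 dyads for Aim 2, so 50 per arm supposes that all are in the randomised cohort. A value of 25 per arm shows smaller arms, because the school cohort was added after ED recruitment problems (section 1.1).

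*1. False pattern, one group alone.* P(pattern) = P(significant rise) × [1 − P(significant)], from the noncentral t with n − 1 degrees of freedom and noncentrality d√n.

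- n = 50, d = 0.28: 0.492 × 0.508 = 0.250. This is the peak.
- n = 50, other values: d = 0.10, 0.092; d = 0.40, 0.165; d = 0.60, 0.014.
- n = 25: the peak is again 0.250, at d = 0.41; d = 0.10 gives 0.064 and d = 0.60 gives 0.147.

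A two-sample t-test of change falsely favours the intervention with probability 0.025 at any common *d*.

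*2. False pattern required in both youth and adults, as 2b is worded.* Simulation with bivariate normal changes, 100,000 runs per cell:

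| Within-dyad correlation of change | 0 | 0.25 | 0.5 | 0.75 | 1 |
|---|---|---|---|---|---|
| n = 50, d = 0.28 | 0.063 | 0.084 | 0.111 | 0.149 | 0.251 |
| n = 50, d = 0.10 | 0.008 | 0.016 | 0.027 | 0.043 | 0.092 |
| n = 25, d = 0.41 | 0.062 | 0.084 | 0.109 | 0.145 | 0.250 |
| Between-arm test, both groups | 0.0005 | 0.002 | 0.005 | 0.009 | 0.025 |

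*3. The no-change part.* P(control rise is non-significant) = 1 − power of the paired test.

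- d = 0.20: 1 − 0.284 = 0.72 at 50 per arm; 1 − 0.161 = 0.84 at 25.
- d = 0.28: 1 − 0.492 = 0.51 at 50; 1 − 0.270 = 0.73 at 25.

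*4. When the intervention truly works.* Probability of the pattern against power of the between-arm test, one group alone:

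| Per arm | True gain, intervention v control (SD) | Pattern | Between-arm test |
|---|---|---|---|
| 50 | 1.0 v 0 | 0.950 | 0.999 |
| 50 | 1.0 v 0.1 | 0.893 | 0.994 |
| 50 | 1.0 v 0.4 | 0.208 | 0.844 |
| 25 | 0.8 v 0.2 | 0.814 | 0.547 |

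The pattern is not uniformly weaker. In the last row it succeeds more often, but partly because the control rise goes undetected.

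**The case against.** The strongest reply is that the plan already intends a between-arm comparison. Read together, sections 1.6 A and 1.6 B say that change in hypertension knowledge will be compared between the randomised arms. Hypothesis 2b is then only a research prediction, natural when control youth complete job-readiness badges, and not a decision rule. No section plans separate tests of knowledge in each arm. This is a declared pilot. The 25% is a worst case that needs equal gains near one particular size and either one group judged alone or perfect within-dyad correlation.

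Much of that stands as a limit on size. The rates are conditional and cannot be tied to this trial, because the documents give no SD or correlation. With both groups required and correlations of 0 to 0.75, the peak at 50 per arm is 6% to 15%. The section 4.7 F sentence is weak evidence too: it does not say which knowledge it means, and it conflicts with 2b only if hypertension knowledge is included.

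It does not dispose of the point. Section 1.6 names no test, follow-up or baseline adjustment, and 6.1, where these belong, is silent. The stated hypothesis remains one that a non-significant control result would appear to confirm. The intent in 1.6 is a reason to bring 2b into line with it. Pilot status excuses the missing power calculation, not a hypothesis that does not use the control arm as a comparator.

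**Conclusion.** The concern holds and should be fixed. Both textual facts are certain: 2b contains no between-arm contrast, follow-up time or margin, and 6.1 names no Aim 2 test for hypertension knowledge. The consequence depends on how 2b is eventually judged. If by separate paired tests, with equal true gains in the two arms, the false-support rate peaks at 25% for one group alone and at 6% to 25% when both are required. The corresponding rates for a between-arm test are 2.5%, and from under 0.1% to 2.5%. A modest control rise would usually pass as no change. These figures assume a two-sided 5% level, 1:1 allocation, and 50 or 25 dyads per arm. The point is confined to a secondary outcome of the randomised ED cohort; the primary blood pressure comparison is not affected.

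**What to change.** For the randomised ED cohort:

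1. Reword 2b, for example: *In the ED cohort, at [1 week or 2 months; sponsor to name one] post-intervention, mean HTN knowledge adjusted for baseline will be higher in the intervention arm than in the control arm, in adults and in youth separately.*
2. Drop the no-change statement for controls, or mark it as an expectation that is not tested.
3. Add to 6.1, for example: *HTN knowledge at that follow-up will be compared between arms by linear regression on group and baseline HTN knowledge, separately for adults and youth. The adjusted difference will be reported with a 95% CI; within-arm changes are descriptive.* Each model then has one person per dyad, so no clustering term is needed.
4. In 4.7 F, say which knowledge is meant, and reconcile it with 2b.

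The school cohort has no control arm ("For the school cohort, we will be looking at changes before and after the 6-week intervention in adult and youth participants"), so this wording does not apply there. Section 6.1 names no knowledge test for that cohort either, and a pre/post analysis should be stated for it separately.

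The cost is wording in 1.1 B, 6.1 and 4.7 F, with no new data or software. Because ED recruitment has begun, the change should be dated and made before knowledge results by arm are examined. The price in precision, before baseline adjustment, is a 95% interval about 1.4 times as wide as a single-arm one. The half-width is t√(2/n) against t/√n: 0.40 against 0.28 SD at 50 per arm, and 0.57 against 0.41 SD at 25.

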Arm 1- Intervention: Participants in the intervention arm will receive the youth-led HTN education digital badge to complete, which will be comprised of a 6-week playlist of one module per week comprising the playlist. Youth will learn from the module and will teach the adult in their dyad about hypertension education in each week's themed module.

Arm 2- Control: For dyads that are randomized into the control arm, the youth will complete job readiness digital badges. These will include a Career & Job Readiness digital badge playlist, with such playlists as, "Interview Preparation", "Resume Ready", and "Professionalism". While this group may complete multiple digital badges, the total time needed to complete the badges will be approximately equivalent to that of the intervention group (eg. one hour per week for each arm).
9. For both arms, youth must submit evidence of completion (eg. photograph, document) as specified in the playlist's instructions. Evidence will be reviewed by the study team and a digital badge is received if all XPs are satisfactorily completed. If not satisfactorily completed, then a note will be sent back to the youth on how to fix or improve the evidence and resubmit.

10. Adult participants in both arms return to RWJUH for follow-up BP check and complete follow-up assessments- blood pressure self-care scale, hypertension knowledge assessment, and self-efficacy to manage hypertension scale. They will receive an incentive for returning at 1 week and 2 months after completion of digital badge. Youth will complete follow-up assessments of hypertension knowledge and confidence in managing blood pressure of adults at the same timepoints but will be done remotely/electronically.

Due to challenges recruiting youth through adults in the ED, we will be adding a cohort to the study. For this new cohort of the study, we will recruit interested youth from NBHSTHS. Students will be asked to pair themselves with an adult (18+) (preference for adult who has been diagnosed with hypertension) with an existing relationship with the student where it would be feasible to complete an online module together 1 hour per week for 6 weeks. The adult must be fluent in English or Spanish and the student must be able to speak the fluent language of the adult. For this cohort, study procedures are as follows:

1. We will recruit students at NBHSTHS for information sessions (see youth recruitment flyer).

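### Hypothesis 2b predicts no change in control-arm HTN knowledge, but Section 6.1 names no knowledge analysis, and a non-significant pre/post t-test could not show it

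*Combined protocol and SAP*

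**What the plan says.** HTN knowledge is a secondary outcome: "we will collect secondary outcomes of HTN knowledge and youth self-efficacy" (Section 1.1). Hypothesis 2b states that "HTN knowledge will increase from pre- to post-intervention in youth and adults in the intervention group and will not change in control group". Each half concerns one arm on its own. Hypothesis 2a, by contrast, predicts a larger fall in BP in one arm than in the other.

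Section 6.1 does not mention HTN knowledge under Aim 2. It describes balance checks at baseline, then BP ("Analysis will include mean BP change from baseline to 2-month follow-up for each arm using a t-test", followed by a regression with a group indicator and baseline BP), and then one further item: "For youth empowerment, pre- and post-intervention data will be compared with significance testing via t-test". It gives no alpha, margin or confidence level, and no rule for deciding whether 2b is supported.

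Section 1.5 calls the study a pilot and leaves the power calculation to later studies. Section 4.3 sets Aim 2 at 100 dyads without dividing them by arm or cohort. Section 1.6 describes the school cohort as before/after only, so it supplies no controls.

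**The concern.** A significance test can reject no change but cannot establish it. The only explicit pre/post tool in Section 6.1 is such a test. The likely way to fill the gap for 2b is to run it in each arm and read a significant result in one and a non-significant result in the other as support for the hypothesis. On that reading, the clause "will not change in control group" becomes easier to support as the control arm gets smaller or the scores noisier.

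Some control gain is plausible, because controls repeat the instrument. For youth, "Youth will complete follow-up assessments of hypertension knowledge and confidence in managing blood pressure of adults at the same timepoints" applies in both arms (Section 1.3 A, step 10), and adults repeat the assessment too. A retest or secular gain could be reported as no change, and the whole pre/post gain in the intervention arm could then be credited to the badge.

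**Working it through.** The plan gives no power, SD, effect size, alpha or margin for HTN knowledge, so it has no figure to reproduce. The check asks how informative a non-significant control-arm test would be if the t-test named for youth empowerment were used.

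**Inputs from the documents**
- 100 dyads for Aim 2 (Section 4.3).
- Two arms, allocation ratio not stated (Section 1.3 A, step 8).
- ED recruitment reported as difficult, which is why the school cohort was added (Section 1.1).

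**Assumptions**
- 1:1 allocation with every dyad from the ED and no dropout, so 100 / 2 = 50 control pairs at most, for youth and for adults separately. Values of 40 and 25 allow for attrition or a smaller ED cohort.
- Two-sided alpha 0.05, paired t-test.
- Pre/post correlation r = 0.5, varied from 0.3 to 0.7.
- True control gain d = 0.25 score SDs, which is half of an assumed 0.5-SD badge gain.

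**Miss rate**

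SD of change = SD × √(2(1 − r)), so the standardised change is dz = d / √(2(1 − r)). The noncentrality is dz × √n. The miss rate is the probability that a noncentral t with n − 1 df falls inside ± t(0.975, n − 1).

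| n | r | dz | dz × √n | critical t | missed |
|---|---|---|---|---|---|
| 50 | 0.5 | 0.25 / 1.000 = 0.250 | 1.768 | 2.010 | 59% |
| 50 | 0.3 | 0.25 / 1.183 = 0.211 | 1.494 | 2.010 | 69% |
| 50 | 0.7 | 0.25 / 0.775 = 0.323 | 2.282 | 2.010 | 39% |
| 40 | 0.5 | 0.250 | 1.581 | 2.023 | 66% |
| 25 | 0.5 | 0.250 | 1.250 | 2.064 | 78% |

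A large control gain would usually be detected. At r = 0.5, a 0.5-SD gain is missed 7% of the time with 50 pairs, 13% with 40 and 33% with 25. The difficulty is with moderate gains.

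**Precision at r = 0.5**

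95% CI half-width = t(0.975, n − 1) × √(2(1 − r)/n).
- n = 50: 2.010 × 1/7.071 = 0.28 SD.
- n = 25: 2.064 × 1/5 = 0.41 SD.

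**Would an equivalence test rescue the clause?**

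Two one-sided 5% tests, true change zero, margins in SDs of the change:
- 50 pairs: power about 35% for a margin of 0.3, 75% for 0.4 and 93% for 0.5.
- 25 pairs: about 2%, 25% and 57%.

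Only a wide margin could be met, so dropping the clause is more sensible than testing it formally.

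**The case against.** The clause can fairly be read as an expectation and not as a claim to be tested. Section 1.1 lists directional predictions without criteria, the outcome is secondary, and Section 1.5 declares a pilot. Formal equivalence testing would be out of proportion. That stands: it limits the severity, and it is why no equivalence test is proposed.

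The harm of crediting the whole intervention-arm gain to the badge also disappears once the arms are compared directly, because a control gain is then subtracted. That stands too, and the between-arm contrast is therefore the centre of the fix. It does not make the no-change clause supportable, so the clause still has to go.

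A reader might infer two stronger points, and the documents support neither:
- **That the plan would treat a non-significant control test as proof of no change.** No such rule is written. The sentence "pre- and post-intervention data will be compared with significance testing via t-test" concerns youth empowerment, and Section 6.1 names no test for HTN knowledge at all. The misreading is left open; it is not prescribed.
- **That Section 4.7 F contradicts 2b.** It says "We have also hypothesized that youth in both arms of the RCT (Aim 2 first cohort) may experience increased knowledge and self-empowerment", but it does not say hypertension knowledge. Control youth complete job readiness badges, so knowledge of another kind is a natural reading.

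**Conclusion.** The point holds in a limited form. Hypothesis 2b contains a no-change claim for the control arm, and Section 6.1 provides no analysis, margin or decision rule for HTN knowledge. Extending the youth empowerment t-test to it would not fill the gap. With the most favourable 50 control pairs, a 0.25-SD control gain would go undetected 59% of the time (69% to 39% across r = 0.3 to 0.7), and the interval around the control change would be ± 0.28 SD. With 25 pairs the figures are 78% and ± 0.41 SD.

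The size rests on assumed alpha, correlation, allocation, retention and effect size, none of which the documents state. The logical point, that non-significance does not show no change, needs none of them. The change is worth making because it alters what the trial can conclude about a named secondary outcome, but nothing here threatens the primary BP comparison.

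**What to change.** - **Section 1.1 B.** Remove the no-change clause from Hypothesis 2b. Restate it as a greater increase in HTN knowledge in the intervention arm than in the control arm, for youth and for adults. This gives 2b the same form as 2a.
- **Section 6.1, between-arm analysis.** Add a between-arm estimate of the difference in knowledge change, adjusted for baseline knowledge, with a 95% CI, separately for youth and adults. The BP regression already in that section is the template. Name which follow-up (1 week or 2 months) it refers to.
- **Section 6.1, control arm.** Report control-arm change descriptively with its 95% CI. State that a non-significant control pre/post test is not evidence of no change.
- **Only if the sponsor wants to claim no change.** Fix and justify a margin in advance. Otherwise no equivalence test is needed.

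The cost is wording in two sections, with no new data, visits or participants. The trial gives up the claim of no change in controls. The between-arm estimate will itself be imprecise. With 50 per arm and no adjustment, a difference of 0.5 SD of change gives 0.5 × √(50/2) = 2.5, and power of about Φ(2.5 − 1.96) = 71%. An estimate with its interval therefore suits a pilot better than a verdict by p-value.
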